The Child Health Questionnaire Parent Form 28-item (CHQ-PF28) (Protocol Appendix 10.11) is evaluated by the primary caregiver at Visit 3 and Visit 6 for the subject's health status and health related quality of life. CHQ-PF28 items have four, five, or six response options, divided over eight multi-item scales (Physical Functioning [PF, Q2.1a–2.1c], Behavior [BE, Q5.1a-5.1c, Q5.2], Mental Health [MH, Q6.1a-6.1c], Self-Esteem [SE, Q7.1a-7.1c], General Health Perceptions [GH, Q1.1, Q8.1a-8.1c], Parental Impact - Emotional [PE, Q9.1a-9.1b], Parental Impact - Time [PT, Q9.2a-9.2b], and Family Activities [FA, Q9.3a-9.3b]) and five single item concepts (Global Health [GGH, Q1.1], Role/Social Limitations - Emotional/Behavior [REB, 3.1], Role/Social Limitations - Physical [RP, Q3.2], Bodily Pain/Discomfort [BP, Q4.1], Global Behavior [GBE, Q5.2], Family Cohesion [FC, Q9.4], and Change in Health [CH, Q8.2]). In addition, the individual scale scores will be aggregated to derive 2 summary component scores: the physical functioning and psychosocial health summary scores. Range on subscales and the overall scale is 0–100, where 0 is the worst possible health state and 100 the best possible health state. Details for item and multi-item scale scoring, calculation of standardized scores and Aggregate Physical and Psychological Summary Scores can be found in the Child Health Questionnaire (CHQ) Scoring and Interpretation Manual (HealthActCHQ).

The Parenting Stress Index – Short Form (**PSI-4-SF**) is a 36-item self-report measure of parenting stress at Visit 3 and Visit 6. Three subscales (Parental Distress [PD: Q1-12], Parent-Child Dysfunctional Interaction [P-CDI: Q13-24], and Difficult Child [DC: Q25-36]) consist of 12 items each. Parents use a 5-point scale to indicate the degree to which they agree with each statement. The subscale score is the sum of the respective item scores. "Total Stress" score is the sum of the 3 subscale scores. The subscale will be set to missing if 2 or more (>1) item scores in the subscale are missing. Total Stress score is set to missing if 1 or more subscale score is missing.

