The **SNAP-IV** (Protocol Appendix 10.7) rating scale includes 18 ADHD and 8 oppositional defiant disorder (ODD) symptoms as specified in the DSM-IV-TR and International Statistical Classification of Diseases and Health Related Problems 10th Revision (ICD-10) Classification of Mental and Behavioral Disorders. The symptoms are scored by assigning a severity estimate for each symptom on a 4-point scale. The SNAP-IV rating is performed by the parent or legal

representative at each visit. The ratings from the SNAP-IV scale are grouped into the following 4 subscales:

- ADHD-Inattention (items #1-9),
- ADHD-Hyperactivity/Impulsivity (items #10-18)
- ODD (items #19-26)
- ADHD-Combined subscale: (items #1 18)

Each subscale score is the average of the available item scores in the subscale. The SNAP-IV rating scale will be administered at Visit 3 and Visit 6.

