6.4 Handling of Dropouts, Missing Data, and Data Discrepancies

For the primary analysis of the primary efficacy endpoint, the frequency of IA behaviors during the treatment (titration + maintenance) period will be calculated over the number of days with non-missing IA diary data in the treatment period. No explicit imputation of missing data will be used, but this approach is implicitly equivalent to using the frequency of IA behaviors during the days with non-missing IA diary data to impute the frequency for days after study discontinuation or days with missing IA diary data. In addition to this implicit imputation, multiple imputations under the assumption of missing at random (MAR) and missing not at random (MNAR) will be used for handling missing data for sensitivity analysis. Details of imputation methods are specified in Section 7.8.2

For analysis of frequency of IA behaviors during the treatment period (titration or maintenance), the following methods will be followed.

1) If subjects discontinued the study during or prior to the maintenance period, their maintenance period will be counted from Visit 5 (exclusive) through the date of last dose as documented on the End of Study eCRF page (inclusive). If the date of last dose is not collected, it will be imputed by the subjects' last visit for the study.

2) If subjects have \geq 7 daily diaries in the maintenance period, their maintenance IA frequencies will be based on maintenance daily diaries.

3) If subjects have <7 daily diaries in the maintenance period, their maintenance IA frequencies will be calculated pooling the titration period diaries with the maintenance period diaries.

4) If subjects do not have any maintenance diaries, their maintenance IA frequencies will be entirely derived from the titration period diaries.

Missing data for secondary efficacy endpoints (investigator CGI-S, investigator CGI-I and caregiver CGI-I) will be handled by using the Mixed Model for Repeated Measures method, which is implemented via SAS[®] PROC MIXED procedure. MMRM assumes data are "Missing At Random (MAR)". That is, the probability that an observation is missing may depend on the observed values but not the missing values in the previously scheduled visits.

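### The SAP keeps a PSI-4-SF subscale with one unanswered item but states only a plain sum, so read literally 11 answers are scored as if they were 12

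*SAP*

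**What the plan says.** SAP 5.2.2 describes the PSI-4-SF as a 36-item parent questionnaire given at Visits 3 and 6, with three subscales that "consist of 12 items each". On the response format it says: "Parents use a 5-point scale to indicate the degree to which they agree with each statement". The scoring formula is: "The subscale score is the sum of the respective item scores". The missing-item rule is: "The subscale will be set to missing if 2 or more (>1) item scores in the subscale are missing". Total Stress adds the three subscales, and "Total Stress score is set to missing if 1 or more subscale score is missing".

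No other section covers the case of one missing item:

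- SAP 6.4 deals with the IA diary and then with the CGI scales: "Missing data for secondary efficacy endpoints (investigator CGI-S, investigator CGI-I and caregiver CGI-I) will be handled" by the repeated-measures model. It does not mention PSI-4-SF.
- SAP 7.8.6.2 specifies an ANCOVA of the Visit 6 score with baseline as covariate. It gives no item-level rule.
- Protocol 5.2.4 describes the instrument but not its handling of missing items.

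The neighbouring questionnaires are covered. For CHQ-PF28, SAP 5.2.2 sends the reader to a named scoring manual. For SNAP-IV it says: "Each subscale score is the average of the available item scores in the subscale". PSI-4-SF has neither provision, and the SAP's reference list contains no PSI scoring source.

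**The concern.** The two PSI-4-SF rules do not fit together. A threshold that tolerates one missing item needs a formula that works with 11 answers. A plain sum does not: the unanswered item contributes nothing, which amounts to scoring it 0.

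The score is used in three places. It is the ANCOVA response at Visit 6, it is the baseline covariate at Visit 3, and Table 14.2.2.4 reports its change from baseline. An item skipped only at Visit 6 would show as a fall in the score, and one skipped only at Visit 3 as a rise. PSI-4-SF is also the third additional secondary endpoint in the fixed testing order. Caregiver CGI-I, SNAP-IV and the two responder endpoints are tested only if it succeeds.

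The double programming in SAP Section 8 would not necessarily catch the problem, because two programmers following the same text would agree with each other.

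**Working it through.** The plan states no PSI-4-SF figure to reproduce, so the check applies the SAP's scoring rule directly.

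**Inputs**

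- Items per subscale: 12 (SAP 5.2.2). Three subscales give 3 × 12 = 36 items, which matches the SAP.
- Score: plain sum. A subscale is kept with 0 or 1 items missing (SAP 5.2.2).
- Item codes: 1 to 5, **assumed**. Protocol Appendix 10.11 prints numeric codes only for items 22, 32 and 33. The other items carry letter responses.
- Share of forms with one item missing in a given subscale: not in the documents. 2% and 5% are **assumed**, with 10% as a wider case.

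**Subscale with one missing item**

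Shortfall = value of the missing item, so 1 to 5 points. The possible range drops from 12–60 to 11–55. If the missing item equals the mean of the other 11, the relative shortfall is 1/12 = 8.3%.

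| Item mean | All 12 items | Sum of 11 | Shortfall | Prorated (sum of 11 × 12/11) |
|---|---|---|---|---|
| 1 | 12 | 11 | 1 | 12 |
| 2 | 24 | 22 | 2 | 24 |
| 3 | 36 | 33 | 3 | 36 |
| 4 | 48 | 44 | 4 | 48 |
| 5 | 60 | 55 | 5 | 60 |

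Proration is exact only when the missing item equals the mean of the answered ones. Take 11 answers averaging 3. If the missing item is 5, the true score is 33 + 5 = 38; the plain sum is 5 low and the prorated score of 36 is 2 low. If the missing item is 1, the true score is 34; the plain sum is 1 low and the prorated score is 2 high. So proration removes the systematic understatement but does not correct every form.

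**Total Stress**

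Up to one item can be missing in each of the three subscales with the total still scored. The shortfall is then 3 × 1 = 3 to 3 × 5 = 15 points on a 36–180 scale, or 3 × 3 = 9 of 108 at mid-scale. If the misses were independent at 2% to 5% per subscale, all three would coincide in 0.02³ = 0.0008% to 0.05³ = 0.0125% of forms.

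**Group mean, per subscale**

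Shift = share × item mean. At an item mean of 3:

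- 2%: 0.02 × 3 = 0.06 points low
- 5%: 0.05 × 3 = 0.15 points low
- 10%: 0.10 × 3 = 0.30 points low

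**Treatment difference at Visit 6**

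A share common to both arms shifts both means equally and largely cancels. If the shares differed, say 5% in one arm and 2% in the other (assumed for illustration), the difference would be off by about (0.05 − 0.02) × 3 = 0.09 points.

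**The case against.** The strongest reply is that the SAP never says in words that 11 items are summed unadjusted. Tolerating one gap is compatible with an unstated substitution. SAP Section 4 promises separate dataset specifications that define derived variables, and these are not available here. That is fair as to what the program will do, and a reader should not infer that the reported scores will certainly be wrong. It does not rescue the text. The SAP gives a formula and a threshold, and together they yield an 11-item sum. Reading one missing item as a missing subscale would contradict the threshold.

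A second reply concerns coding and direction. A reader might infer that a skipped item makes parenting stress look lower and so reads as improvement. The SAP does not state the scoring direction. The three printed code sets do not all run the same way: for item 22, 5 is the unfavourable end, and for item 32, 1 is. The 1 to 5 coding and the meaning of a lower score are therefore assumptions. This objection stands as a limit. Under 0 to 4 coding the shortfall would be 0 to 4 points.

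A third reply is that nothing shows an effect on the treatment comparison. This also stands. The documents give no reason to expect item non-response to differ by arm, and the form asks parents to answer every statement. PSI-4-SF is tested only after CGI-S, investigator CGI-I and CHQ-PF28 have all succeeded.

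Finally, proration is not the only remedy, and the SNAP-IV rule belongs to another instrument. Both are true. SNAP-IV shows only that the SAP elsewhere uses a formula that adjusts for a skipped item.

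**Conclusion.** The point holds, as a minor one. Followed literally, SAP 5.2.2 gives an incorrect PSI-4-SF subscale score whenever exactly one item is unanswered. Under assumed 1 to 5 coding, each affected subscale is 1 to 5 points low, about 3 points at an item mean of 3. At the assumed 2% to 5% of forms, the shift in a group mean is 0.06 to 0.15 points. The main consequence is added noise in the Visit 6 response and the baseline covariate.

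Two stronger readings are not supported. The first is that the rule biases the treatment effect or threatens the testing sequence; that would need item non-response to differ by arm, which the documents neither show nor suggest. The second is that Total Stress is materially affected. Its shortfall can reach 15 points rather than the mid-scale 9, but only in the rare case of a gap in every subscale. Total Stress is also only summarised in SAP 7.8.6.2; the listed endpoints in SAP 5.2.2 are the three subscales.

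**What to change.** Before unblinding, add to SAP 5.2.2: when exactly one item is missing, the subscale equals 12 times the mean of the 11 answered items, after any reverse coding; when two or more are missing, the subscale is missing; Total Stress is the sum of the resulting subscales. If the instrument's own scoring rule differs, cite that rule and follow it instead. State the item codes and scoring direction in the same place.

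The cost is a sentence or two in the SAP and one line in the derivation program and its independent check. The existing threshold stays, and no further data are needed.

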5.3 Pharmacokinetic Variables

Not applicable

5.4 Safety Variables

5.4.1 *Medical History and Adverse Events (AEs)*

AEs that occur on/after signing ICF will be recorded on the AE CRF. Medical history and AEs will be coded for preferred term (PT) and system organ class (SOC) using Medical Dictionary for Regulatory Activities (MedDRA). AEs are evaluated by the investigators for seriousness, relationship, and severity.

5.4.2 *Prior, Concomitant, and Prohibited Medications*

Prior medications and concomitant medications will be extracted from the Prior/Concomitant Medication CRF. Medications taken prior to Study Day 1 will be considered as prior medications and medications taken on or after Study Day 1 will be considered as concomitant medications. Prior and concomitant medications will be coded using WHO Drug Dictionary (WHODD) for PT and Anatomical Therapeutic Chemistry (ATC) classification.

Prohibited medications include, but are not limited to,

- α_2 -adrenergic agonists (e.g. clonidine and guanfacine) used for any other reason except for monotherapy treatment for ADHD
- Anti-psychotics including aripiprazole, risperidone, quetiapine, and ziprasidone
- Anticonvulsants including carbamazepine and valproic acid, antidepressants, mood stabilizers including lithium, benzodiazepines, cholinesterase inhibitors or any drug known to inhibit CYP2D6 activity
- Herbal supplements

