## 4.1.1 Inclusion Criteria

- 1. Healthy male or female subjects, age 6 to 12 years at the time of screening.
- Diagnosis of ADHD according to the Diagnostic and Statistical Manual of Mental Disorders- 5 (DSM-5 confirmed by the Schedule for Affective Disorders and Schizophrenia for School-aged Children – Present and Lifetime Version 2013 (K-SADS-PL 2013).
- 3. Retrospective Modified Overt Aggression Scale (R-MOAS) score of  $\geq$ 24 at screening.
- 4. CGI-S score of at least moderately ill at both Screening and Randomization.
- 5. Vitiello Aggression Scale score from -2 to -5 at Screening.
- 6. Free of antipsychotic medication for at least two weeks prior to Visit 2.
- 7. Monotherapy treatment with FDA-approved optimized ADHD medication (psychostimulant or non-stimulant) at an FDA-approved dose for at least one month prior to Screening, and willing to maintain that dose throughout the Baseline and Treatment period.
- α 2- adrenergic agonists (e.g. clonidine and guanfacine) used for any other reason except for monotherapy treatment for ADHD (e.g. aggression or insomnia) must be discontinued at least two-weeks prior to Visit 2.
- 9. Medically healthy and with clinically normal laboratory profiles, vital signs, and electrocardiograms (ECGs).
- 10. Weight of at least 20 kg.
- 11. Able and willing to swallow tablets whole and not chewed, cut or crushed.
- 12. Written Informed Consent obtained from the subject's parent or legal representative, and written Informed Assent obtained from the subject if appropriate.
- 13. Measurement of compliance  $\ge$  80% for completion of IA Diary during Baseline Period.

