#### Table 1: Schedule of Visits and Procedures

Phase	se Pre-treatment		Treatment				Conversion/
Period	od Screening Baseline		Tit	Titration Maintenance			Taper
VISIT NUMBER	1	2	3	4	5	6	7
DAY	-45	-15	1	8	15	36	43
WINDOW (DAYS)	≤45d prior to Visit 3	≥15d prior to Visit 3	Oc	7d±2d from Visit 3	14d±2d from Visit 3	21d±3d from Visit 5	7d±1d from Visit 6
Informed Consent/Assent a	X b						
R-MOAS, K-SADS-PL 2013 & Vitiello Aggression Scale	х						
Medical History	Х		X d				
Demographics	Х						
Physical Examination	Х					Х	
ECG (12-lead)	Х			Х		Х	
Inclusion/Exclusion Criteria	Х						
Randomization			X b,e				
Urine Drug Screen	Х		Х				
Urine Pregnancy Test f	Х		х				X
Diary Training & Distribution or Evaluation		Х	X e	Х	Х	Х	
Vital Signs g	Х						Х
Weight, height, BMI	Х		Х	Х	Х	Х	Х
Hematology/chemistry/Urinalysis	Х		Х			Х	Х
PK Blood Sampling				X h	X h		
Columbia Suicide Severity Rating Scale (CSSRS)	Х		Х	Х	Х	Х	Х
Investigator CGI-S	Х		Х	Х	Х	Х	
Caregiver and investigator CGI-I				Х	Х	Х	
Efficacy scales (SNAP-IV, CHQ-PF28, PSI-4-SF)			Х			Х	
Safety Scales (Simpson-Angus, Barnes, AIMS)			Х	Х	Х	Х	Х
Infrequent Behaviors Checklist			Х	Х	Х	Х	
Adverse Events			Х	Х	Х	Х	Х
Concomitant Medications	Х	Х	х	Х	Х	Х	Х
Drug Dispensation			X b		Х	Х	

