Visit 2 will occur at least 15 days prior to Visit 3. Please note that, per protocol and within the EDC, Visit 1 and Visit 2 may occur on the same day.

- 1. Provide training for IA diary and dosing diary module
- 2. Distribute device
- 3. Assess and record concomitant medications

## 4.2.3 Visit 3

Visit 3 will occur at least 15 days following Visit 2 according to the Schedule of Visits and Procedures.

- 1. Administer efficacy scales (SNAP-IV, CHQ-PF28, PSI-4-SF)
- 2. Assess IA diary compliance / review training as necessary
- 3. Confirm eligibility to randomize to study medication treatment
- 4. Randomize subject via IWRS
- 5. Administer Investigator CGI-S
- 6. Administer Infrequent Behaviors Checklist
- 7. Administer safety scales (Simpson-Angus, Barnes Akathisia, AIMS)

Supernus® Pharmaceuticals, Inc. 810P302

- 8. Record height, weight, and BMI
- 9. Collect blood samples for hematology/chemistry
- 10. Collect urine samples for urinalysis, urine drug screen (all subjects), and pregnancy test (FOCBP only)
- 11. Administer C-SSRS
- 12. Record concomitant medication
- 13. Assess for any clinically significant change in Medical History
- 14. Dispense SM via IWRS.
- 15. Review training on dosing diary module
- 16. Assess adverse events (post-dose)

#### 4.2.4 Visit 4

Visit 4 will occur 7 (±2) days following Visit 3 according to the Schedule of Visits and Procedures.

- 1. Administer Investigator CGI-S
- 2. Administer caregiver and investigator-completed CGI-I
- 3. Administer Infrequent Behaviors Checklist
- 4. Administer safety scales (Simpson-Angus, Barnes Akathisia, AIMS)
- 5. Record height, weight, and BMI
- 6. Perform 12-lead ECG
- 7. Collect blood samples for PK analysis
- 8. Administer C-SSRS
- 9. Record concomitant medication
- 10. Review IA diary compliance and provide training as required
- 11. Collect AEs
- 12. Review dosing diary compliance and provide training as required

## 4.2.5 Visit 5

Visit 5 will occur 14 (±2) days following Visit 3 according to the Schedule of Visits and Procedures.

- 1. Administer Investigator CGI-S
- 2. Administer caregiver and investigator-completed CGI-I
- 3. Administer Infrequent Behaviors Checklist
- 4. Administer safety scales (Simpson-Angus, Barnes Akathisia, AIMS)
- 5. Record height, weight, and BMI
- 6. Collect blood samples for PK analysis
- 7. Administer C-SSRS
- 8. Record concomitant medication
- 9. Review IA diary compliance and provide training as required
- 10. Collect AEs

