## 5.4.1.2 Recording and Evaluation of Adverse Events

All subjects who are enrolled (starting at Visit 3) will be questioned regarding the occurrence of AEs. At each contact with the subject, the investigator must seek information on AEs by specific questioning and, as appropriate, by examination. Information on all AEs should be recorded immediately in the source document, and also in the appropriate adverse event module of the eCRF. All clearly related

signs, symptoms, and abnormal diagnostic procedures results should be recorded in the source document, though they may be grouped under one diagnosis. For example, fever, elevated WBC, cough, abnormal chest X-ray, etc., can all be reported as "pneumonia".

All AEs occurring after enrollment and throughout the study period must be recorded. A treatmentemergent adverse event (TEAE) is defined as an AE with a start date on or after the first dose of study drug, or that worsened following first administration of study drug. For subjects who receive SM, TEAEs will be collected starting from the first dose of SM. The clinical course of each AE should be followed until resolution or until, in the medical judgment of the Investigator, the event has stabilized or is assessed as chronic.

An increase in the CSSRS, Simpson Angus Scale, Barnes Akathisia Scale, or the AIMS will not necessarily be rated as an AE unless the event meets AE criteria.

The Investigator is responsible for evaluating AEs and determining the following:

- Serious vs. Non-serious: Is the event a Serious Adverse Event (SAE)?
- Causality: Was AE related or possibly related to the SM?
- Severity: How pronounced is the incapacity/discomfort caused by an AE?

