# 6.3 Analysis Populations

The population of "all enrolled subjects" consists of all those screened subjects who meet the requirements for study participation and are entered in the Baseline period of the study. The population of "all randomized subjects" consists of all those enrolled subjects who complete the Baseline Period, meet the inclusion/exclusion criteria and are randomized.

Safety Population: will include all randomized subjects who received at least 1 dose of study drug.

Intent-to-Treat (ITT) Population: will include all subjects who received at least 1 dose of study drug and have a baseline and at least 1 valid post-randomization assessment of frequency of IA behaviors based on IA diary entry.

Per-Protocol (PP) Population: will include all of the subjects in the ITT population who completed the treatment period with 80% diary completion compliance and who did not have major protocol deviations.

PK population: will include all subjects in the safety population who had at least one PK sample drawn which had a quantifiable concentration for at least one analyte of interest.

The safety, ITT, PP, and PK populations are based on randomized treatment received.

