# 6.13.1 Adverse Events

AEs will be classified into standardized medical terminology from the verbatim description (Investigator term) using the Medical Dictionary for Regulatory Activities (MedDRA). AEs will be summarized using discrete summaries at the subject and event level by system organ class and preferred term for each treatment group. Similarly, treatment-emergent AEs will be summarized by severity and relationship separately. Verbatim description and all MedDRA level terms, including the lower level terms, for all AEs will be contained in the subject data listings.

All AEs occurring after randomization and throughout the study period will be recorded. For subjects who receive SM, treatment-emergent AEs (TEAEs) will be collected starting after the first dose of SM (Visit 3) to the end of the study. These AEs include those that emerge during treatment or worsen in severity during treatment. These AEs will be tabulated, listed and analyzed.

Separate TEAE incidence tables will be presented for the three treatment groups. The incidence rates for all SADRs will also be summarized as described for all TEAEs.

In addition, these same tables will be presented by treatment period (Titration, Maintenance, and combined Titration and Maintenance). For the combined Titration and Maintenance Periods, the incidence of TEAEs will also be presented by highest severity reported and the dose of SM at first occurrence.

Listings (and tabular summaries, if warranted) of deaths, other SAEs, and other significant TEAEs, including TEAEs resulting in treatment discontinuation, will be provided.

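### The SAP counts adverse events from consent, but the protocol and both visit schedules first ask about them on Day 1, so no adverse event enquiry is scheduled before the first dose

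*SAP*

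**What the plan says.** **Start of AE recording.**
- SAP 5.4.1: "AEs that occur on/after signing ICF will be recorded on the AE CRF".
- Protocol 5.4.1.2: "All subjects who are enrolled (starting at Visit 3) will be questioned regarding the occurrence of AEs". The same section adds: "All AEs occurring after enrollment and throughout the study period must be recorded".
- Protocol 6.13.1: "All AEs occurring after randomization and throughout the study period will be recorded".
- Protocol 4.2.3, the Visit 3 procedure list: "Assess adverse events (post-dose)".

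**Schedules.** The "Adverse Events" row in protocol Table 1 and in the SAP's schedule (SAP 3.2) is marked at Visits 3, 4, 5, 6 and 7 and blank at Visits 1 and 2. The procedure lists in protocol 4.2.1 and 4.2.2 contain no AE step.

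**Meaning of *enrolled*.** Protocol 6.3 defines enrolled subjects as "all those screened subjects who meet the requirements for study participation and are entered in the Baseline period of the study", which places enrolment at Visit 2; SAP 7.1 agrees. The SAP's terminology table (Section 4) defines it as having signed consent. Protocol 5.4.1.2 ties it to Visit 3.

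**Related rules.** Protocol 5.4.1.2 counts as treatment-emergent both events that start on or after the first dose and earlier events that get worse after it. Protocol 5.4.2.1 requires serious AEs to be reported within 24 hours of awareness and names no date from which the duty begins. SAP 5.4.6 schedules physical examinations at Visits 1 and 6 and says clinically significant findings are reported as AEs.

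**The concern.** The SAP describes a dataset that the visit schedule does not produce. The SAP supersedes the protocol's analysis methods, but it does not instruct sites. Sites work from the protocol's visit lists, and those hold no AE question until after the first dose.

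Three things depend on this. First, the part of the treatment-emergent definition that concerns worsening needs a record of the event and its severity before dosing. Second, SAP 6.4.1 fills vague start dates with the first-dose date: this happens when the year is unknown, and also when the year matches and the month is missing or matches. An event that began before dosing, but was first asked about afterwards and dated loosely, can therefore become treatment-emergent by rule. Third, serious events before dosing have no stated collection start and no clear place in the outputs. SAP 7.9.1 tabulates AEs by titration, maintenance, the two combined, and tapering. The AE listings in SAP Appendix 2 use the Safety Population, which requires a dose.

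**Working it through.** **1. How many start points are there in practice?** Protocol 4.3.6 has subjects randomised and starting to dose during Visit 3. Visit 3, randomisation and post-dose at Visit 3 are therefore all essentially Day 1. That leaves two positions in conflict, plus an ambiguous term:

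| Source | AE start |
|---|---|
| SAP 5.4.1 | Consent |
| Protocol 5.4.1.2 (questioning), 6.13.1, 4.2.3 and both schedules | Day 1 |
| Protocol 5.4.1.2 (recording, after enrolment) | Consent, Visit 2 or Day 1, depending on which definition of *enrolled* is used |

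**2. Length of the gap.** Inputs from the protocol synopsis (duration), Table 1 and 4.2.2: screening up to 30 days; baseline at least 15 days; pre-treatment phase at most 45 days; Visits 1 and 2 may fall on the same day; last visit on Day 43.
- Plan's own figure: 30 + 15 = 45 days, which reproduces the stated maximum.
- Day 1 to Day 43: 43 − 1 = 42 days.
- Longest gap: 45 / (45 + 42) = 45 / 87 = 52% of scheduled time.
- Shortest gap (Visits 1 and 2 together, 15-day baseline): 15 / (15 + 42) = 15 / 57 = 26%.
- Scheduled AE enquiries: 0 in the pre-treatment phase; 5 from Visit 3 onward.

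**3. Could an excluded drug be stopped after consent?** Inclusion criterion 6 reads "Free of antipsychotic medication for at least two weeks prior to Visit 2". Criterion 8 sets the same two weeks for alpha-2 agonists used other than as ADHD monotherapy.
- Latest stop before Visit 3: 14 + 15 = 29 days.
- Time available after consent: at most 45 − 29 = 16 days. It is zero if Visits 1 and 2 coincide.

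The windows permit it. Nothing in the documents says how often, or whether, it happens.

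**4. What pre-dose reference exists?** The schedule gives medical history at Visit 1 with an update at Visit 3 for clinically significant change; C-SSRS and laboratory tests at both; extrapyramidal scales at Visit 3; and concomitant medications at Visits 1 to 3. These give partial cover. None of them is an AE record with onset and severity.

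**The case against.** One can argue for the plan that a Day 1 start is coherent. Protocol 5.4.1 defines an AE in terms of a subject who has been given a product, so the SAP sentence may be the outlier, and amending it would also reconcile the texts. Protocol 5.4.1.2 asks investigators to seek AE information at every contact. Protocol 4.2 tells families to call in abnormalities between visits and allows unscheduled visits in all study periods. Protocol 5.4.2.1 covers all serious AEs without setting a late start. The eCRF is not available to us, and it may accept pre-dose entries. An event asked about late can still carry its true onset date, and any misclassification would fall on both blinded arms.

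Much of this stands. It limits the size of the problem and rules out four stronger readings that a reader might infer:
- *Several separate start times.* Most of them are Day 1 in different words (step 1).
- *Children going through drug withdrawal unobserved.* The windows allow a stop after consent but do not show one. Criterion 6 describes a state that a child may have reached long before screening.
- *Half the study, and 92 children, without AE follow-up.* The 52% is an upper bound. The 92 is 398 − 306, a difference of two approximate targets, and would include children who fail at Visit 1 after almost no time under observation.
- *Biased treatment-emergent comparisons.* No difference between arms is shown, and most such events start after dosing in any case.

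The rest does not close the gap. Changing the SAP to Day 1 would align the words but leave pre-dose events uncollected and SAP 5.4.6 without a matching AE step at Visit 1. The every-contact instruction follows a sentence that begins questioning at Visit 3, and the call-in route relies on families to volunteer events.

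**Conclusion.** The inconsistency is real and should be corrected. The SAP promises AEs from consent. The protocol and both schedules provide for enquiry from Day 1, after the dose, and *enrolled* has three meanings. Under the schedule as written, no AE enquiry takes place for about 15 to 45 days, or 26% to 52% of scheduled time to Day 43.

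The consequences are an AE record that is not collected uniformly, a weak pre-dose reference for events that worsen on treatment, and a serious-AE rule with no start date. The effect on treatment-emergent comparisons is likely small; the loss is mainly in pre-dose AEs and serious AEs. This rests on two assumptions: that sites follow the visit lists, and that the eCRF, which is not in the documents, does not prompt for AEs at Visits 1 and 2.

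**What to change.** - Choose one AE start point and one meaning of *enrolled*, and apply both in SAP 5.4.1, SAP Section 4 (terminology), SAP 7.1, and protocol 4.2.3, 5.4.1.2, 6.3 and 6.13.1. Consent is the simplest choice because SAP 5.4.1 already states it.
- Mark AEs at Visits 1 and 2 in both schedules (two cells in each, four in all) and add an AE step to protocol 4.2.1 and 4.2.2.
- Make the Visit 3 enquiry cover the time before the first dose as well as after it.
- State in protocol 5.4.2.1 that serious-AE reporting runs from the same start point.
- Keep treatment-emergent events counted from the first dose. List pre-dose AEs and serious AEs separately, including those of subjects who are never dosed.

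**Cost.** Wording changes in both documents and a modest number of extra AE entries at visits that already exist. The change cannot recover data for children already past those visits; for them, the study report should say that pre-dose AEs were not systematically sought.
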